### **9.1.2 Imputation**

Unless otherwise noted, data will not be imputed.

### **9.1.3 Daylight Savings Time Adjustments**

On March 10, 2019 at 2:00 am the clocks change to 3:00 am for Daylight Savings Time. All clinic procedures for the remainder of the treatment period will be moved forward by one hour after daylight savings time occurs. All duration calculations for times post-daylight savings time that will be relative to a time prior to daylight savings will need to be programmatically adjusted for the hour that was lost on the morning of March 10.

### **9.1.4 Descriptive Statistics**

Unless otherwise indicated, continuous variables will be summarized with the following descriptive statistics: n (number of observations), (arithmetic) mean, SD, min, median, and max.

Categorical data will be summarized with frequencies and percentages. Percentages by categories will be based on the number of subjects exposed within a treatment.

For categorical data the categories will be presented in the tables exactly as they appear in the CRF.

### **9.1.5 Pooling**

Summary statistics will be calculated by treatment (and timepoint, if applicable).

### **9.1.6 Unscheduled Measurements**

Unscheduled and early termination measurements will be included in the listings. With the exception of unscheduled measurements used for baseline, unscheduled measurements will be excluded from the descriptive statistics and statistical analysis.

## **9.2 Analysis Data Definitions**

### **9.2.1 Baseline Definition**

Unless otherwise stated, baseline for post-dose evaluations within each period is defined as the last observation recorded before the first study drug administration in each period. The last observation can be an unscheduled / repeated measurement. If a pre-treatment observation is missing in a given period then the screening value may be used.

## 9.2.2 Treatment/Subject Grouping

Label	Grouping
Study Drug	Balovaptan, matching placebo for balovaptan, moxifloxacin, matching placebo for moxifloxacin
Treatment	A: 10mg balovaptan B: 50mg balovaptan C: 400mg moxifloxacin on day 2 D: 400mg moxifloxacin on day 15
Dose Level	10mg balovaptan, 50mg balovaptan, 400mg moxifloxacin

## 9.2.3 Common Variable Derivations

Variable	Data Type	Definition/Calculation
Change from baseline	All	Post-dose Observation minus baseline Observation within period
Change from baseline relative to placebo	TT-Doppler Echocardiogram Parameters	Change from baseline for the treatment C or D period minus the change from base for the treatment A or B period
Analysis Study Day (Prior to first Dose)	All	Date of Measurement minus Dose Date
Analysis Study Day (Post first Dose)	All	Date of Measurement minus Dose Date +1

## 9.2.4 QC

The analysis datasets and the TFLs will be QC'd according to the general PRA EDS QC plan.

### 9.2.4.1 Critical Data

The QC plan requires datasets be classified as critical or non-critical. As the objectives of this study are to characterize the pharmacokinetics and assess safety and tolerability the datasets considered critical are subject level, pharmacokinetic, and adverse events (ADSL, ADPC, ADPP, and ADAE).

## 9.2.5 ADaM Datasets and Metadata

The analysis datasets will be generated in accordance with Clinical Data Interchange Standard Consortium (CDISC) Analysis Data Model (ADaM) Version 2.1.

ADaM compliant datasets will be delivered to the sponsor. A define.xml file version 2 with the corresponding metadata will be included. Analysis results metadata are excluded.

## 9.3 Software

The statistical analysis and reporting will be done using [SAS® for Windows™ Version 9.4](#) or higher (SAS Institute, Inc.).

PK parameter calculations will primarily be done using [Phoenix® WinNonlin®](#) version 8.1 or higher (Certara, L.P.). Additional PK computations may be performed in [SAS®](#).

## 9.4 Statistical Methods

### 9.4.1 Statistical Outlier Determination

No statistical outlier analysis is planned.

### 9.4.2 Predetermined Covariates and Prognostic Factors

There are no predetermined covariates or prognostic factors.

### 9.4.3 Hypothesis Testing

No formal hypothesis testing will be done.

## 9.5 TFL Layout

Table shells are provided with and approved as part of this SAP. Small changes to shell layout due to the nature of the data may be required after lock at the discretion of the PRA project statistician. Other changes to the shells may be out of scope. The TFLs will be provided as a single document in Adobe PDF format (in Letter format), and as individual files for each table, figure or listing in Rich Text Format (.rtf).

## 10.0 Analysis Sets

Analyses	Safety Set	PK Set
Disposition Summaries	✓	✓
Baseline Characteristics	✓	✓
Safety Assessments	✓	
Pharmacokinetic Concentrations	✓	
Pharmacokinetic Parameters		✓

### 10.1 Safety Set

The Safety Set will consist of subjects who are randomized and receive at least one dose of study drug (either balovaptan, moxifloxacin or matching placebo), whether prematurely withdrawn from the study or not. This set will be used for the safety data summaries, baseline characteristic summaries, and PK concentration summaries. This set will be analyzed as treated.

### 10.2 Pharmacokinetic Set

The PK Set will consist of all subjects in the safety set with the exception of subjects who significantly violated the inclusion or exclusion criteria, deviated significantly from the protocol, or have unavailable or incomplete data. This set will be analyzed as treated.

## 11.0 Subject Disposition

The number and percentage of subjects randomized, dosed, and members of each analysis set will be presented. The number and percentage of subjects who withdrew from the study prematurely and a breakdown of the corresponding reasons for withdrawal will also be presented.

## 12.0 Protocol Deviations

Protocol deviations will be included in the CSR.

## 13.0 Demographic and Baseline Characteristics

### 13.1 Demographics

Subject demographics will be summarized by analysis set. The summary will include the subjects' age (years), sex, race, ethnicity, weight (kg), height (cm), and BMI (kg/m^2).

All demographic data as collected during the screening visit will be listed by subject.

### 13.2 Medical History

Medical history, categorized by preferred term according to MedDRA, will be listed by subject.

## 14.0 Concomitant Medications

Concomitant medications, categorized by medication group and subgroup according to WHO Drug Dictionary, will be listed by subject. Medications with an end date prior to the first dose of study drug will be considered prior medications and will be noted in the listing. If a partial date allows a medication to be considered concomitant it will be categorized as such.

## 15.0 Treatment Compliance and Exposure

The number of subjects receiving each dose of study drug will be summarized by visit.

Exposure data will be listed by subject.

## 16.0 Pharmacokinetic Analyses

### 16.1 Pharmacokinetic Variables

Concentrations of balovaptan, M2, M3, and moxifloxacin will be collected in plasma.

PK parameters of balovaptan, M2 (as appropriate), M3, and moxifloxacin will be calculated for plasma.

### 16.2 Plasma Pharmacokinetic Summaries

#### 16.2.1 Plasma Concentrations

Plasma concentrations for balovaptan, M2 (as appropriate), M3, and moxifloxacin below the quantifiable limit (BQL) will be set to 0 in the computation of mean concentration values. Descriptive statistics (n, arithmetic mean, geometric mean, SD, coefficient of variation, median, min, and max) will be used to summarize the plasma concentrations by treatment and visit for balovaptan and by treatment for moxifloxacin at each scheduled timepoint. If over ½ the subjects in a given cell have values BQL then the descriptive statistics will not be presented and will instead display as BQL for the mean and min. With the exception of min and max, all other statistics will be missing.

Linear and semi-logarithmic plots of the arithmetic mean plasma concentration by scheduled sampling time will be provided by treatment for balovaptan on day 1 and day 14 and by treatment for moxifloxacin on day 2 for treatment C and day 15 for treatment D. These plots will show time in hours. The plots will match the summary table results and will not have an observation at a given timepoint if more than half of the subjects have values BQL.

Linear and semi-logarithmic plots of the individual plasma concentration by actual sampling time will be provided by subject (one subject per page). These plots will show time in hours. Individual plots will use the BQL handling procedure described below for "Plasma Pharmacokinetic Parameters".

All individual subject plasma concentration data will be listed by subject.

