6.6 PHARMACOKINETIC ANALYSES

Subjects will be excluded from the PK analysis population if they significantly violate the inclusion or exclusion criteria, deviate significantly from the protocol, or if data are unavailable or incomplete. Excluded cases will be documented together with the reason for exclusion. All decisions on exclusions from the analysis will be made prior to database closure.

Pharmacokinetics are a secondary objective of this study. The specific objectives are

- To investigate the pharmacokinetics of balovaptan, M2 (as appropriate), and M3.
- To investigate the pharmacokinetics of moxifloxacin.

Individual plasma concentrations at each sampling timepoint for balovaptan, M2 (as appropriate), M3, and moxifloxacin will be presented by listings and descriptive summary statistics by treatment, including means, geometric means, ranges, standard deviations and coefficients of variation. Individual and mean concentration versus time will be plotted on linear and semi-logarithmic scales.

PK parameters will be estimated using standard non-compartmental methods. All PK parameters for balovaptan, M2 (as appropriate), and M3 will be presented by individual listings and summary statistics by treatment including means, geometric means, medians, ranges, standard deviations and coefficients of variation.

The following balovaptan, M2 (as appropriate), M3 PK parameters will be estimated:

- Cmax: Day 1 and Day 14 for Treatment A and B
- AUC0-24h: Day 1 and Day 14 for Treatment A and B
- Tmax: Day 1 and Day 14 for Treatment A and B
- Ctrough: Day 11, 12, 13, 14 for Treatment A and B
- Time to steady state for Treatment A and B

The following moxifloxacin PK parameters will be estimated:

- Cmax, AUC0-24h, and Tmax will be estimated on Days 2 (Treatment C) or 15 (Treatment D)

Additional PK analyses maybe be conducted as appropriate for balovaptan, M2 (as appropriate), M3 and moxifloxacin.

Subjects will be excluded from the PK analysis population if they significantly violate the inclusion or exclusion criteria, deviate significantly from the protocol, or if data are unavailable or incomplete. Excluded cases will be documented together with the reason for exclusion. All decisions on exclusions from the analysis will be made prior to database closure.

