### 16.2.2 Plasma Pharmacokinetic Parameters

Plasma PK parameters for balovaptan, M2, M3, and moxifloxacin will be estimated using non-compartmental methods with WinNonlin®. The plasma PK parameters will be estimated from the concentration-time profiles, and AUCs will be calculated using linear up / log down. In estimating the PK parameters, BQL values at the beginning of the profile will be set to zero. BQL values that occur after the first quantifiable point will be considered missing. Values that are embedded between BQLs, or quantifiable values occurring after two or more BQLs, will be set to missing at the discretion of the pharmacokineticist. Actual sampling times, rather than scheduled sampling times, will be used in all computations involving sampling times. If the actual time or dose time is missing, the scheduled time may be substituted in order to calculate the PK parameter.

Parameter	Description	Analytes	Treatment: Day	SAS Programming Notes
Cmax	Maximum plasma concentration. Observed peak analyte concentration obtained directly from the experimental data without interpolation, expressed in concentration units	All	A: 1 and 14 B: 1 and 14 C: 2 D: 15	Cmax from WNL
Tmax	Time to maximum plasma concentration. First observed time to reach peak analyte concentration obtained directly from the experimental data without interpolation, expressed in time units.	All	A: 1 and 14 B: 1 and 14 C: 2 D: 15	Tmax from WNL
AUC0-24	Area under the plasma concentration-time curve from time 0 to 24 hours post-dose.  If the actual 24 hr concentration was taken at or after 24 hr post-dose then AUC0-24 will be calculated by WNL to 24 hr.  If the actual 24 hr concentration was taken before nominal 24 hr and a valid $\lambda z$ is available then the data will be extrapolated to 24 hr.  If the actual 24 hr concentration was taken before 24 hr and a valid $\lambda z$ is not available, then AUC0-24 hr will be calculated to actual time closest to 24 hr within 10% of 24 (i.e., $t > 21.6$ hr)  If the actual 24 hr concentration was not taken and the last sample was taken prior to the nominal 24 hr and a valid $\lambda z$ is not available then AUC0-24 hr	All	A: 1 and 14 B: 1 and 14 C: 2 D: 15	AUC0-24 from WNL where partial time =24, if missing for a subject then AUC at nominal time 24 hr from summary file is used for AUC0-24

	will not be calculated.			

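### SAP 16.2.1 sets BQL concentrations to zero and also reports their geometric mean, which is then zero, undefined, or based on fewer subjects than the n beside it

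*SAP*

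**What the plan says.** SAP section 16.2.1 (Plasma Concentrations) makes three statements that bear on each other.

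- Substitution: values "below the quantifiable limit (BQL) will be set to 0 in the computation of mean concentration values".
- Statistics: "Descriptive statistics (n, arithmetic mean, geometric mean, SD, coefficient of variation, median, min, and max) will be used to summarize the plasma concentrations" at each scheduled time.
- Suppression: "If over ½ the subjects in a given cell have values BQL then the descriptive statistics will not be presented". A cell with anything from one BQL value up to exactly half is still printed.

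Protocol section 6.6 also asks for concentration summaries "including means, geometric means, ranges, standard deviations and coefficients of variation", and gives no BQL rule.

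Two other SAP rules could be thought to fill the gap. Section 9.1.2 says only "Unless otherwise noted, data will not be imputed". Section 16.2.2 has a different convention, under which BQL values at the start of a profile are zero and "BQL values that occur after the first quantifiable point will be considered missing". That convention is for the non-compartmental parameters and, by reference from 16.2.1, for the individual plots. It does not apply to the concentration summary table.

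**The concern.** A geometric mean is defined only for positive values. One zero makes the product, and so the geometric mean, equal to zero; on the log scale the calculation fails because the logarithm of zero does not exist. A rule that inserts zeros does not fit a statistic that cannot take them, and the SAP does not say what should happen.

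Three outputs are possible for the same cell: 0, missing, or a value computed on the quantifiable subjects only. In the third case, two means in one row describe different sets of subjects under a single n, and the geometric mean can be the larger of the two, which cannot happen when both come from the same data. The geometric mean is a planned summary in both documents, so the choice should not be left to the software's default.

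**Working it through.** The plan states no figure on this point, so there is nothing to reproduce. The check is algebra.

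**Inputs from the documents.** BQL = 0 and suppression only above one half (SAP 16.2.1). 48 evaluable subjects, all of whom receive A and B, with half receiving C and half D (SAP 6.0 and 6.1). A cell is therefore about 48 subjects for A or B, and about 24 for moxifloxacin under C or D.

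**Inputs not in the documents (assumed).** Quantifiable concentrations are log-normal, with a between-subject CV of 20% to 150%. The LLOQ and the BQL frequency are unknown.

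**Step 1, zeros kept.** GM = (x₁ × … × xₙ)^(1/n). One xᵢ = 0 gives GM = 0. By GM = exp(mean of ln xᵢ) it is undefined. This holds for 1 to 24 BQL values of 48; from 25 the cell is suppressed.

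**Step 2, zeros dropped.** Let q be the BQL share and let the quantifiable values have log-mean μ and log-variance s² = ln(1 + CV²).

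- Arithmetic mean with zeros: AM = (1 − q) × exp(μ + s²/2)
- Geometric mean without zeros: GM = exp(μ)
- GM exceeds AM when q > 1 − exp(−s²/2) = 1 − 1/√(1 + CV²)

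For CV 30%: 1 − 1/√1.09 = 4.2%. For CV 50%: 1 − 1/√1.25 = 10.6%. For CV 100%: 1 − 1/√2 = 29.3%.

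| CV | BQL share above which GM > AM | BQL subjects needed, n = 48 | n = 24 |
|---|---|---|---|
| 20% | 1.9% | 1 | 1 |
| 30% | 4.2% | 3 | 2 |
| 50% | 10.6% | 6 | 3 |
| 100% | 29.3% | 15 | 8 |
| 150% | 44.5% | 22 | 11 |

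Every threshold lies below the one-half cut-off, so such cells would be printed.

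**Step 3, example.** Median 20 (arbitrary units), CV 30%, n = 48. The mean of the quantifiable values is 20 × √1.09 = 20.88. With 3 BQL, AM = 45/48 × 20.88 = 19.58; with 12 BQL, 36/48 × 20.88 = 15.66; with 24 BQL, 24/48 × 20.88 = 10.44. In each case GM is 0 or undefined with zeros kept, and 20.00 with zeros dropped.

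**Step 4, size at a fixed BQL share.** At 40% BQL, GM/AM = 1/(0.6 × √(1 + CV²)). This is 1.60 at CV 30%, 1.18 at CV 100% and 0.92 at CV 150%. With no variability at all it would be 1/0.6 = 1.67, which is the upper limit at that share.

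**The case against.** **The zero rule may mean the arithmetic mean only.** That reading is possible. The geometric mean would then have no BQL rule at all, so the gap remains.

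**The shells may settle it.** SAP 9.5 makes the table shells part of the approved SAP, and Appendix 5 places them in a separate document that is not available here. They could carry an NC convention or a BQL count. This stands as a limit on what can be confirmed; if the shells have such a rule, 16.2.1 should state it too.

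**Mixed cells may not occur.** This also stands. Protocol 1.2.1.1 describes rapid absorption, with a median Tmax of 1 to 4.5 h after single fasted doses, and no LLOQ is given. Some BQL values at 0.5 and 1.0 h on Day 1 are plausible, above all for M2 and M3, which must first be formed. The documents do not show that they will arise.

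**Carry-over.** A reader might infer that the Day 1 pre-dose cells for A and B in Periods 2 and 3 are affected, because only some subjects have drug left over. The documents do not support this. Summaries are by treatment and visit, not by period. Only 4 of 12 sequences place A directly after B (BAC, CBA, BAD, DBA), and 4 of 12 place B directly after A (ABC, CAB, ABD, DAB). Assume equal allocation and nothing quantifiable after an intervening placebo period. Even if every direct follower were quantifiable, 8/12 = 67% of the cell would be BQL, and it would be suppressed.

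**Moxifloxacin.** A reader might also count the moxifloxacin tables as affected. Protocol 4.5.10 has those samples analysed only if the assay sensitivity test fails. SAP 16.1 does not repeat that condition. The example applies only if the samples are analysed.

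**Little depends on it.** This is correct. The mean plots use arithmetic means, the PK parameters have their own BQL rule, the steady-state evaluation models individual log troughs from Days 11 to 14, and the QTc analyses belong to a separate SAP (section 5.0). Individual concentrations are listed and plotted.

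**Conclusion.** The concern holds, at the level of a wording correction. As written, the zero rule and the geometric mean are incompatible in any printed cell with one BQL value up to half BQL. The result is 0 or undefined, or, if zeros are dropped, a figure on a reduced and undisclosed n.

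The thresholds for the reversed order of the means rest on log-normality and on the CV range shown. A single BQL value does not generally reverse the order: for one BQL value the CV must be below about 21% at n = 48 or about 30% at n = 24. That affected cells will occur is itself an assumption. A reader might go further and infer that exposure, steady-state or QTc conclusions are at risk. They are not, because none of those analyses uses these geometric means.

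**What to change.** In SAP 16.2.1, limit the zero substitution to the arithmetic mean, SD, CV and median. Add that the geometric mean is not calculated, and is shown as NC, for any cell containing a BQL value. Print the number of BQL values beside n in the concentration tables, and carry the same convention into the shells. The rule for cells that are more than half BQL can stay as it is.

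The cost is one sentence in the SAP and one column in the shells. The downside is that no geometric mean will appear at a few early time points if BQL values occur there; the median and the BQL count still describe those cells.

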### 16.2.2 Plasma Pharmacokinetic Parameters

Plasma PK parameters for balovaptan, M2, M3, and moxifloxacin will be estimated using non-compartmental methods with WinNonlin®. The plasma PK parameters will be estimated from the concentration-time profiles, and AUCs will be calculated using linear up / log down. In estimating the PK parameters, BQL values at the beginning of the profile will be set to zero. BQL values that occur after the first quantifiable point will be considered missing. Values that are embedded between BQLs, or quantifiable values occurring after two or more BQLs, will be set to missing at the discretion of the pharmacokineticist. Actual sampling times, rather than scheduled sampling times, will be used in all computations involving sampling times. If the actual time or dose time is missing, the scheduled time may be substituted in order to calculate the PK parameter.

Parameter	Description	Analytes	Treatment: Day	SAS Programming Notes
Cmax	Maximum plasma concentration. Observed peak analyte concentration obtained directly from the experimental data without interpolation, expressed in concentration units	All	A: 1 and 14 B: 1 and 14 C: 2 D: 15	Cmax from WNL
Tmax	Time to maximum plasma concentration. First observed time to reach peak analyte concentration obtained directly from the experimental data without interpolation, expressed in time units.	All	A: 1 and 14 B: 1 and 14 C: 2 D: 15	Tmax from WNL
AUC0-24	Area under the plasma concentration-time curve from time 0 to 24 hours post-dose.  If the actual 24 hr concentration was taken at or after 24 hr post-dose then AUC0-24 will be calculated by WNL to 24 hr.  If the actual 24 hr concentration was taken before nominal 24 hr and a valid $\lambda z$ is available then the data will be extrapolated to 24 hr.  If the actual 24 hr concentration was taken before 24 hr and a valid $\lambda z$ is not available, then AUC0-24 hr will be calculated to actual time closest to 24 hr within 10% of 24 (i.e., $t > 21.6$ hr)  If the actual 24 hr concentration was not taken and the last sample was taken prior to the nominal 24 hr and a valid $\lambda z$ is not available then AUC0-24 hr	All	A: 1 and 14 B: 1 and 14 C: 2 D: 15	AUC0-24 from WNL where partial time =24, if missing for a subject then AUC at nominal time 24 hr from summary file is used for AUC0-24

	will not be calculated.			
Ctrough	Predose concentration prior to each daily dose from Day 11 to Day 14	Balovaptan, M2, M3	A: 11 to 14 B: 11 to 14	Taken directly from the observed plasma concentration-time data

Descriptive statistics (n, mean, geometric mean, SD, %CV, median, min, and max) will be used to summarize the calculated PK parameters by treatment. For Tmax, only median, min and max will be presented.

